## 8.0 Consent/Accent Process

- 8.1 A trained study team member will obtain informed consent from all adult participants and all parent/legal guardians of child participants. The trained study team member will also obtain assent from all children. If a parent or legal guardian chooses to enroll more than one child in the study, the consent and assent process will be completed for each child enrolled. Children ages 4-14 will be assented using the Assent Script. Children ages 15-17 will be assented using the Consent Script. There will be minor differences in assent discussions depending on children's ages, as study team members will use age-appropriate language.

If the study team does not have a supply of BinaxNOW tests, or if a potential participant is unwilling or unable to complete at-home BinaxNOW testing, the Lollipop Only consent and assent will be used.

## PROTOCOL TITLE: SAFE AND HEALTHY SCHOOLS

The consent process will occur in person whenever possible. When needed, the consent may occur over the phone. The assent process will always occur in person, at the school, after the parent or legal guardian has provided consent.

The consent process will be conducted face to face whenever possible. If needed, it may be conducted with parents or legal guardians over the phone. The consent informs participants that email is generally not a secure way to communicate, as there are many ways for unauthorized users to access email. It instructs participants to avoid sending sensitive, detailed personal information by email. It also says that subjects may participate in the study even if they do not consent to email communication. At this time during the consent process, study staff will ask and record on the data collection form whether or not the parent or legal guardian consents to email communication. Consent scripts will be provided in person, by mail, or by email, per the participant or parent's preference.

There will not be any waiting period between informing the prospective participant and obtaining the consent. Study team members will ensure that parents and legal guardians will not feel pressured to participate. When initially approaching subjects about the research participation opportunity, the study team will emphasize that there is no penalty for choosing not to participate. If parents or legal guardians indicate that they feel rushed, do not have time to fully consider the decision, or they can't ask all their questions, then study team members will encourage them not to enroll. Assent will be sought after obtaining consent from a parent or legal guardian.

A trained study team member will ask questions about key elements of the consent and assent to ensure the potential participant is understanding. Based on their responses to the questions, the study team member will determine whether a potential participant understands the information.

At the beginning of the virtual or at-home study visit for BinaxNOW testing, the study team member conducting the visit will remind the participant and their parent (in the case of children) that participation in research is voluntary. Virtual visits will be conducted using a UW-approved videoconferencing platform.

We will be following HRP-090 – SOP – Informed Consent Process for Research. In accordance with the SOP, the consent script used for this study is the same as the consent form used for the long form of consent documentation, except the signature block has been removed.

## PROTOCOL TITLE: SAFE AND HEALTHY SCHOOLS

Consent scripts and information sheets for adult participants and for parents or legal guardians of children participants are uploaded in ARROW. An assent script is also uploaded.

- 8.2 This research involves no greater than minimal risk to adults or children, and it involves no procedures for which written documentation of consent is normally required outside of the research context. Therefore, we are requesting a waiver of written consent and assent documentation. We will use consent and assent scripts to obtain verbal consent and assent, and we will provide an information sheet to the consenting guardian in person and/or via email or mail. We will document in the study's secure database that verbal consent and assent occurred prior to any study procedures. We anticipate that parents or legal guardians may have someone else pick their child up from schools, such as a grandparent or older sibling. Therefore, the ability to obtain consent verbally over the telephone is essential to be able to conduct this study. To keep in-person and phone consent processes consistent by using a script, we request a waiver of written consent and assent documentation for all participants.

### ***Non-English-Speaking Participants***

We will enroll Spanish-speaking families. The consent script has been translated into Spanish by a translator employed by UW Health Translation Services. Ideally, the study coordinator will be fluent in Spanish so that they can read the consent and assent scripts, solicit and answer any questions, and directly obtain verbal consent and assent. If the study coordinator is not fluent in Spanish, they will use the services of a translator. In that case, the study coordinator would conduct the consenting discussion and solicit questions in English, and the translator would relay this information to the participant in Spanish. In other words, the questions would be translated to English for the study coordinator, and the study coordinator's responses would be translated back to Spanish. If this process is conducted with a parent or legal guardian over the phone and a translator is required, the process would occur as described above.

### ***Participants who are not yet adults (children)***

We will obtain assent from all children who enroll in this study. If they do not assent, we will not enroll them. The study coordinator conducting assent will have sufficient experience and/or training in working with children in this age range. They will use age-appropriate language to inform children that participating in research

## PROTOCOL TITLE: SAFE AND HEALTHY SCHOOLS

studies is voluntary, meaning it is entirely up to them if they want to be in the study. They will be told that no one on the study team will be upset or disappointed if they do not wish to participate. The child will be asked directly if they would like to participate, and they will need to verbally answer in the affirmative. Passive resignation will not be considered assent. Study coordinators will receive training from experienced study staff in recognizing and responding to children's dissent.

Individuals under the age of 18 are considered "children" for the purposes of this study. We will enroll students 4 to 19 years old.

Since no greater than minimal risk to children is presented by this study, we will obtain permission from one parent or legal guardian, even if another parent is alive, known, competent, reasonably available, and shares legal responsibility for the care and custody of the child.

Permission will be obtained from legal guardians, as determined by the school.

Assent will be obtained from all children enrolled in the study.

Assent will be obtained using a verbal script. The Assent Script will be used for children ages 4-14, and the Consent Script will be used for children ages 15-17. If children choose to participate, their verbal assent will be documented in the study's secure database.

## 9.0 Process to Document Consent in Writing

- 9.1 We will not document consent in writing. However, we will document that both consent and assent, when applicable, occurred prior to study procedures in the Data Collection Form in the ICTR version of REDCap.
- 9.2 This research involves no greater than minimal risk to adults or children, and it involves no procedures for which written documentation of consent is normally required outside of the research context. Therefore, we are requesting a waiver of written consent and assent documentation. Consent and assent scripts have been uploaded in ARROW.

## 10.0 Setting

## PROTOCOL TITLE: SAFE AND HEALTHY SCHOOLS

10.1 Research procedures will be performed at elementary schools and virtually. We have received approval from the Madison Metropolitan School District. If enrollment targets are not met, we will seek approval from additional area school districts. If a participant is unable to complete a virtual visit, the study procedures will take place in person, at the participants' homes. Study team members will be in private, quiet locations whenever conducting virtual study visits.

Since we are conducting research in elementary schools, we will seek approval from school districts. We will submit documentation from an appropriate authority at each school or district granting permission to conduct the human subjects research. We will contact each school or district to obtain this permission and meet the requirements each site may have for conducting human subjects research.

## 11.0 Study Intervention

- 11.1 The “lollipop” swab collection method and the BinaxNOW COVID-19 Ag Card Home Test are being evaluated. The PCR testing method, the COVID-Flu Multiplex Assay, may also be included in this study. This test provides results for COVID-19, Influenza A, and Influenza B.
- 11.2 Study team members will store, handle, and guide administration of the “lollipop” collection swab. They will instruct participants to suck on the swab for 20 seconds, as they would suck on a lollipop. The study team member will closely oversee that the participant is following instructions.

Study team members will provide all participants who consent to at-home antigen testing with a BinaxNOW COVID-19 Ag Card Home Test kit, which includes two tests and instructions in both English and Spanish. A trained study team member will supervise the test via video chat or in person. For Spanish-speaking participants/parents, the study team member supervising the test will either be fluent in Spanish, or they will use the services of a translator.

- 11.3 The “lollipop” collection swab is a non-significant risk device. It does not meet the definition of “significant risk,” which is a device that presents a potential for serious risk to health, safety or welfare of subjects.

The saliva sample collected from the “lollipop” will be analyzed by Exact Sciences Laboratories using the COVID-Flu Multiplex Assay. The FDA approved this assay for use with nasal swabs under the Emergency Use Authorization (EUA) only. The saliva samples collected from the “lollipop” may also be analyzed by ACL using either their standard process for COVID-19 PCR testing or a multiplex assay.

The BinaxNOW COVID-19 Ag Card Home Test received EUA from the FDA. The test is authorized for prescription home use with self-collected observed direct anterior nasal swab samples from individuals aged 15 years or older who are suspected of COVID-19 by their healthcare provider within the first seven days of symptom onset or adult-collected nasal swab samples from individuals aged four years or older who are suspected of COVID-19 by their healthcare provider within the first seven days of symptom onset. The BinaxNOW COVID-19 Ag Card Home Test is to be performed only with the supervision of a telehealth proctor. Documentation of the EUA, including an updated Letter of Authorization, have been submitted to the IRB.

## 12.0 Study Timelines

12.1 Participation in the study will typically last from 12-72 hours, depending on when the at-home BinaxNOW test virtual visit is completed. When scheduling virtual visits, we will try to schedule as close as possible to 24 hours after the initial in-school test. The target window is no sooner than 12 hours and no later than 72 hours after the in-school test. If it is not completed within 72 hours, the study team will ask the participant to schedule a time to complete the at-home test as soon as possible. If the participant is not able to complete the at-home test within 5 days of enrollment, they will be withdrawn from the study.

We anticipate enrolling all study participants by August, 2022. We intend to complete primary analyses by October, 2022.

## 13.0 Procedures Involved

13.1 Study Design: This is a quantitative community-based study, conducted in the K-12 setting with school children 4-19 years old, teachers, and staff.

If a participant's initial at-school BinaxNOW test is **positive**, then they will only complete the lollipop swab for PCR testing. They will NOT do the at-home BinaxNOW test virtual visit.

If a participant's initial at-school BinaxNOW test is **negative**, then they will complete both the lollipop swab for PCR testing AND an at-home BinaxNOW test approximately 24 hours later.

If the study team does not have any BinaxNOW tests due to a supply shortage, or if a potential participant is unwilling or unable to complete at-home BinaxNOW testing, the BinaxNOW procedures will be dropped and only the lollipop swab will be collected.

## PROTOCOL TITLE: SAFE AND HEALTHY SCHOOLS

### 13.2 Schedule of Study Procedures

Study Activity	At school or by phone*	At school	Virtual or Home Visit**
Informed Consent	X		
Assent		X	
Collect Basic Information	X		
BinaxNOW test	X***		
Lollipop swab		X	
BinaxNOW test			X***
Adverse Event Assessment		X	X***

\*All adult study participants will provide informed consent and basic information at school. For children participants, the parent or legal guardian may provide consent and basic information either over the phone or in person.

\*\*Only participants who have a negative at-school BinaxNOW test will be asked to do an at-home BinaxNOW test.

\*\*\*If the study team runs out of BinaxNOW tests, or if a participant is unwilling or unable to complete at-home BinaxNOW testing, these study procedures will not be performed. Participants will be consented for the Lollipop-Only alternative.

13.3 Immediately after consent/assent, the study coordinator will collect information about the participant (name, date of birth, gender, race, and ethnicity), as well as the parent or legal guardian's name, in the case of children. The study coordinator will also collect the participant's physical and mailing addresses, phone number, and email address. If participants provide their email address, the study coordinator will ask if they are willing to be contacted about this study in the future. The study coordinator will verbally ask questions and record responses via real-time electronic data capture in ICTR REDCap.

If the study coordinator is unable to collect data directly in REDCap, such as if there is no internet connection or ICTR REDCap is down, then the study team will enter data according to an emergency back-up protocol. For this protocol, the study team may record answers electronically in a PDF version of the data collection form. They may temporarily store PDF files locally on an encrypted laptop computer managed by UW-Madison Department of Pediatrics Computer Services. As soon as possible, study team members would enter data and upload the PDF into REDCap, then immediately delete the file from local storage. The local laptop storage will serve as a transfer proxy, rather than a storage location. Whenever this emergency protocol for data collection is followed, the study team will also follow a sanitation protocol to ensure that the PDF is stored only in REDCap. For sanitation, the PDF will be permanently deleted by the end of the following business day, once the primary data collection method becomes available. The PDF files will be stored locally in a folder specifically set up to be excluded from

## PROTOCOL TITLE: SAFE AND HEALTHY SCHOOLS

the client's backup routine. If files are accidentally backed up, they will be manually removed from the backup and deleted permanently from all locations except REDCap. Additionally, the SMPH VPN via the Palo Alto Global Protect client, configured and available for use on all DOP endpoints, will be enabled and connected by the end-user on data collection endpoints whenever study data is being accessed or transferred.

The study team will make every effort to enter data directly into REDCap in real time. The study team will use a wireless hotspot for reliable internet connectivity, rather than relying solely on the school's Wi-Fi connection, to minimize the need for this emergency data collection protocol.

After this basic information is collected, the study coordinator will begin testing. If the participant did not already receive an at-school BinaxNOW test, then the study coordinator will collect the nasal swab for and administer the BinaxNOW test. When study staff collect the nasal swab for the BinaxNOW test, they may encourage parents/legal guardians to comfort their child. Participants under the age of 18 will only receive nasal swabs when their parent or legal guardian is physically present. If a potential participant is unwilling to have the study team collect a nasal swab, they will not be enrolled in the study.

Next, the study coordinator will guide the participant through completing a "lollipop" swab at school. The lollipop swab is obtained by having the participant suck on a swab for 20 seconds in the same way that they would suck on a lollipop. The study coordinator will ask whether they prefer the PCR nasal swab or lollipop collection method. The study coordinator will provide the lollipop swab to Exact Sciences or ACL for analysis. For Exact Sciences, it will be labeled with the study ID and date of collection. For ACL, lollipop samples will have a label and accompanying requisition form that will both contain the subject's full name, date of birth, and the date and time of collection.

If the study team does not have any BinaxNOW tests due to a supply shortage, study participation will end after the lollipop swab is collected. If BinaxNOW tests are available and the participant intends to do the at-home antigen testing, then the at-school antigen testing is required.

If a participant's initial at-school BinaxNOW test was **positive**, then their study participation is complete after providing the lollipop swab for PCR testing.

If a participant's initial at-school BinaxNOW test was **negative**, then they will be asked to complete an at-home BinaxNOW test approximately 24 hours later.

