### 5.0 Inclusion and Exclusion Criteria

#### 5.1 Eligibility Screening:

This study will enroll MMSD school children ages 4-19 and MMSD staff who currently have at least one symptom of COVID-19, have not had a positive COVID test within the past 3 months, and will undergo nasal PCR testing at an MMSD elementary school.

If symptomatic MMSD school children or staff intend to have nasal swab PCR tests at school, then school-approved personnel may inform adults—staff or children’s parents—of our research study. The staff will either provide a flyer or verbally let them know it involves a lollipop test at that time, and if the at-school BinaxNOW is negative, it will also involve the performance of an at-home BinaxNOW test in approximately 24 hours. If the school does not conduct a BinaxNOW test, then the study team will collect a nasal swab for the “at-school” BinaxNOW test.

If the study team does not have any BinaxNOW tests due to a supply shortage, the at-school and at-home BinaxNOW tests will be dropped and participants will be recruited for a Lollipop Only alternative. Additionally, if a potential participant expresses interest in the study but is unwilling or unable to do at-home BinaxNOW testing, then the study coordinator will offer them the Lollipop Only alternative.

School-approved personnel will also let potential participants know that they would not be eligible to participate if they have had a previous positive COVID-19 test in the past 3 months, either verbally or by providing a flyer. The staff will ask if the adult is interested in speaking to a study coordinator to learn more about the study. If yes, the staff will either direct the potential participant to the study coordinator or they will inform the study coordinator that a potential participant is interested in speaking with them, and they will connect the coordinator to the potential participant, either on the phone or in person.

Alternatively, the study team may gently approach potential participants near the at-school testing locations. Potential participants may also directly contact the study team in response to poster and flyer advertisements.

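### Section 13.3 turns away from the whole study anyone who declines a study-collected nasal swab, although Lollipop Only needs no such swab, so some usable Aim 2 pairs and preference answers are forgone

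*Combined protocol and SAP*

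**What the plan says.** Eligibility in section 5.1 is limited to symptomatic students and staff who "will undergo nasal PCR testing at an MMSD elementary school", so every participant has accepted one nasal swab from the school. A second, study-collected swab arises only when the school has run no antigen test. Section 13.3 puts it this way: "If the participant did not already receive an at-school BinaxNOW test, then the study coordinator will collect the nasal swab". The same paragraph then sets the bar: "If a potential participant is unwilling to have the study team collect a nasal swab, they will not be enrolled in the study". It makes no exception for Lollipop Only.

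Lollipop Only has two stated triggers, repeated in 5.1, 8.1, 13.1 and the 13.2 footnote. One is a shortage of kits. The other is the case where an interested person "is unwilling or unable to do at-home BinaxNOW testing, then the study coordinator will offer them the Lollipop Only alternative". In either case, according to 13.1, "the BinaxNOW procedures will be dropped and only the lollipop swab will be collected". Later in 13.3 the at-school test is made conditional: "If BinaxNOW tests are available and the participant intends to do the at-home antigen testing, then the at-school antigen testing is required".

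Two further rules bear on children. Section 13.3 states: "Participants under the age of 18 will only receive nasal swabs when their parent or legal guardian is physically present". Section 8.2, which foresees that someone other than the parent may collect the child, states that "the ability to obtain consent verbally over the telephone is essential to be able to conduct this study".

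For Aim 2, sections 5.3 and 20.3 require a nasal PCR result and a lollipop PCR result, and no BinaxNOW result. The preference question is asked at the lollipop step in 13.3, after the bar has taken effect. Section 5.1 says that nothing is recorded about people who decline enrolment.

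**The concern.** The bar refers to the study as a whole, but the swab it concerns serves only the BinaxNOW part. A person who declines home testing is enrolled with no study swab. A person who would do the home test and declines only the extra swab at school is turned away. Both have had the school PCR swab and both could suck the lollipop swab.

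Two things are at stake in Aim 2. Each person turned away is a nasal-lollipop PCR pair not collected. Acceptability is also one of the four primary objectives, and its comparative measure is a stated preference between the PCR nasal swab and the lollipop. Removing people because they will not have another nasal swab selects on a trait close to that outcome. Because decliners are not tracked, the selection could not be measured or corrected afterwards.

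**Working it through.** **The plan's own figure.** The only powered number is N=358 for Aim 1 (section 20.2: NPV 91% against 95%, one-sided 0.05, 90% power). The normal approximation gives n = [(1.645·√(0.91·0.09) + 1.282·√(0.95·0.05)) / 0.04]² = 351.6, so 352. The exact binomial gives 358 as the smallest n: reject at 335 or more of 358, with alpha 0.0487 and power 0.909. The figure reproduces. Refusers have no at-school BinaxNOW result, so they count toward neither the 358 nor the 50 positives, and sections 4.3 and 20.2 continue enrolment until both are filled.

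**Rules side by side, where the school ran no BinaxNOW and kits are available**

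- Declines home testing: Lollipop Only under 5.1 and 13.1, with no study swab.
- Declines the study swab and the home test: 5.1 offers Lollipop Only, while 13.3 read literally bars enrolment.
- Declines the study swab but would do the home test: barred by 13.3, and no Lollipop Only trigger names this person.
- Child consented by phone with no parent present: the study swab cannot be taken, and no sentence states what follows.

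**Size, on assumptions.** The documents give neither the share s of people arriving without a school BinaxNOW nor the proportion r of those who decline the study swab and are turned away. I assume s from 10% to 100% and r from 2% to 20%. Then:

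- share turned away: f = s·r
- pairs lost per 450 enrolled: 450·f/(1−f)
- widening of confidence intervals: √(1/(1−f))
- understatement of lollipop preference: f·(q−p), where p is the preference among enrollees and q that among those turned away

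Bias A takes q = 100% and p = 60%, the largest possible bias at that p. Bias B takes q = 95% and p = 65%. All four values are assumptions.

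| s | r | f | Pairs lost | CI width ratio | Bias A (points) | Bias B (points) |
|---|---|---|---|---|---|---|
| 10% | 2% | 0.2% | 0.9 | 1.001 | 0.08 | 0.06 |
| 10% | 20% | 2% | 9.2 | 1.010 | 0.8 | 0.6 |
| 50% | 10% | 5% | 23.7 | 1.026 | 2.0 | 1.5 |
| 100% | 10% | 10% | 50.0 | 1.054 | 4.0 | 3.0 |
| 100% | 20% | 20% | 112.5 | 1.118 | 8.0 | 6.0 |

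Example, third row: f = 0.5·0.1 = 0.05; 450·0.05/0.95 = 23.7; √(1/0.95) = 1.026; 0.05·(1−0.60) = 2.0 points; 0.05·(0.95−0.65) = 1.5 points.

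**The case against.** The strongest reply is that the passages can be read together. Their triggers differ: home testing in 5.1, a study-collected school swab in 13.3. Since 13.3 requires the at-school test only of those who intend home testing, the bar can be taken to govern the BinaxNOW path alone. The home test is itself a nasal swab, so many who refuse another at school will refuse it at home too and already have a route. This stands. It makes the matter an unreconciled gap rather than a flat contradiction, and it shrinks r. It does not remove the problem, because the sentence speaks of the study as a whole and a coordinator following it literally loses the participant.

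A reader might infer that nasal-swab-averse people in general are screened out of the acceptability comparison by 13.3. The documents do not support that. Anyone averse to every nasal swab is already ineligible under 5.1, and the bar adds only those who tolerate the school swab and refuse a further one.

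A reader might also infer that phone-consented children are excluded. They are not: a child whose parent is absent is not unwilling, and where the school or its laboratory partner runs BinaxNOW no study swab is needed. Such a child might even be counted as unable to do the home test, because 13.3 makes the at-school test a condition of it. The protocol simply does not state their route.

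Finally, the selection works against the lollipop hypothesis, so it would not manufacture a finding of greater acceptability, and section 20.4 sets no acceptability threshold for it to cross. That also stands.

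**Conclusion.** The point holds in a limited form. Taken literally, 13.3 discards people who could supply everything Aim 2 needs, and it does so on tolerance of a further nasal swab. It applies only where the school ran no BinaxNOW. The result is some Aim 2 precision forgone and a tendency to understate lollipop preference.

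The documents do not fix the size. The range in the table, from under 0.1 to 8 points and from about 1 to 113 pairs per 450 enrolled, rests wholly on assumed shares and preferences. A reader might take 3 or 6 points (Bias B at 10% or 20% refusal) as the bias in the primary objective. Those figures describe only the group without a school BinaxNOW and scale with its unknown share: 1.5 or 3 points at a 50% share, 0.3 or 0.6 at 10%.

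Neither the 358 nor the 50 is threatened. The case for changing the text is that the change is cheap and removes an avoidable selection step that the study could not measure.

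**What to change.** Reconcile 13.3 with the Lollipop Only provisions.

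- In 13.3, limit the bar to the BinaxNOW part. Say that a person who declines the study-collected at-school swab, or who cannot be given it under the existing parent-presence rule, is offered Lollipop Only. Leave the parent-presence rule as it is.
- State this as a third route to Lollipop Only in 5.1, 8.1, 13.1 and the 13.2 footnote.
- Record the reason for Lollipop Only, and report Aim 2.1 preference with and without this group, so that any selection effect is visible.

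The cost is protocol wording, one REDCap field and a few more lollipop PCR assays. The Lollipop Only consent and assent in 8.1 already exist, and the Aim 1 sample size and analysis set are untouched.
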